10.2.4. Severity

The severity of adverse events (including test findings classified as adverse events) will be graded using the current version of the NCI-CTCAE v5.0 (Division of Cancer Treatment and Diagnosis [DCTD], 2020). TEAEs that are evaluated as CTCAE grade 3 or 4 will be collected in addition to treatment-emergent SAEs and treatment-emergent AESIs as discussed above.

Treatment-emergent AEs, treatment-emergent SAEs, or treatment-emergent AESIs not listed in the NCI-CTCAE will be graded according to the scale in [Table 5](#).

Table 5: NCI-CTCAE Severity Grading System for Adverse Events (v5.0)

Grade	Severity	Description
1	Mild	Asymptomatic or mild symptoms; clinical or diagnostic observations only; intervention not indicated
2	Moderate	Minimal, local, or noninvasive intervention indicated; limiting age appropriate instrumental activities of daily living (ADL)*
3	Severe	Severe or medically significant but not immediately life threatening; hospitalization or prolongation of hospitalization indicated; disabling; limiting self-care ADL†
4	Life-threatening	Life threatening consequences; urgent intervention indicated
5	Death	Death related to adverse events

*Instrumental ADL refers to preparing meals, shopping for groceries or clothes, using the telephone, managing money, etc.

† Self-care ADL refers to bathing, dressing, and undressing, feeding self, using the toilet, taking medications, and not bedridden.

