Always report the diagnosis as the AE term. When a diagnosis is unavailable, report the primary sign or symptom as the AE term with additional details included in the narrative until the diagnosis becomes available. If the signs and symptoms are distinct and do not suggest a common diagnosis, report them as individual entries.

Laboratory results, vital signs, and other diagnostic results or findings should be appraised by the investigator to determine their clinical significance and whether they fulfil the criteria of TEAEs (grade 3 or 4), treatment-emergent SAEs, or treatment-emergent AESIs and will need to be reported. Isolated abnormal laboratory results, vital sign findings, or other diagnostic findings (ie, not part of a reported diagnosis) should be reported as TEAEs if they fulfill reporting criteria for the study (ie, treatment-emergent SAE, treatment-emergent AESI, TEAE [grade 3 or 4]) or require corrective treatment.

For events that are serious due to hospitalization, the reason for hospitalization must be reported as the serious adverse event (diagnosis or symptom requiring hospitalization). A procedure is not an AE or SAE, but the reason for the procedure may be an AE or SAE. Pre-planned (prior to signing the informed consent form [ICF]) procedures, treatments requiring hospitalization for pre-existing conditions that do not worsen in severity, and admission for palliative or social care should not be reported as SAEs (see Section 10.2 for definitions).

For deaths, the underlying or immediate cause of death should always be reported as an SAE.

Any treatment-emergent SAE that may occur subsequent to the reporting period (end of study) that the investigator assesses as related to study drug should also be reported.

All treatment-emergent SAEs, treatment-emergent AESIs, and pregnancies are to be reported according to the procedures in Section 10.1.3.

Note that patient-reported outcome (PRO) data (eg, patient-reported questionnaires, surveys, and instruments) are generally not reportable as individual AEs. However, if the investigator is made aware of any AE that (in his or her judgement) is related to study drug, the AE will be reported and recorded as described in Section 10.1.2.

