10.2.2. Serious Adverse Event

An SAE is any untoward medical occurrence that at any dose:

- Results in **death** – includes all deaths, even those that appear to be completely unrelated to study drug (eg, a car accident in which a patient is a passenger).

- Is **life-threatening** – in the view of the investigator, the patient is at immediate risk of death at the time of the event. This does not include an adverse event that had occurred in a more severe form, might have caused death.
- Requires in-patient **re-hospitalization** (readmission after discharge) or **prolongation of existing hospitalization**. In-patient hospitalization is defined as a hospital admission (any duration) or an emergency room visit for longer than 24 hours. Prolongation of existing hospitalization is defined as a hospital stay that is longer than was originally anticipated for the event or is prolonged due to the development of a new adverse event as determined by the investigator or treating physician.
- Results in persistent or significant **disability/incapacity** (substantial disruption of one's ability to conduct normal life functions).
- Is a **congenital anomaly/birth defect**
- Is an **important medical event** – Important medical events may not be immediately life-threatening or result in death or hospitalization, but may jeopardize the patient or may require intervention to prevent one of the other serious outcomes listed above (eg, intensive treatment in an emergency room or at home for allergic bronchospasm; blood dyscrasias or convulsions that do not result in hospitalization; or development of drug dependency or drug abuse).

Criteria for reporting SAEs must be followed for these events.

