5.7.1. Adverse Events

Summaries that include frequencies and proportions of patients reporting AEs will include the PTs and the SOCs.

An overview of adverse events will be provided by treatment group and for combined dose groups of R10933+R10987, including:

- Total number of TEAEs, SAEs, Total number of AESIs, Serious AESIs, Grade 3 or 4 TEAEs, as well as
- The number and percentage of patients with
 - any TEAE, any SAE, any AESI, any serious AESI, any grade 3 or grade 4 TEAE, any fatal TEAEs, any TEAEs leading to withdrawal from the study, any TEAEs leading to study infusion discontinuation, and any TEAEs leading to study infusion interruption.

Summaries of SAEs and AESIs by treatment group and for combined R10933+R10987 doses will include number (n) and percentage (%) of patients with at least :

- Treatment-emergent AE by SOC and PT
- Treatment-emergent AE by SOC and PT and CTCAE grade

- Treatment-emergent AE related to study treatment by SOC and PT
- Treatment-emergent SAE by SOC and PT
- Treatment-emergent AESIs presented by SOC and PT
- Treatment-emergent grade 3 or 4 AEs presented by SOC and PT

Counts will be provided according to treatment group for each PT within each SOC. Percentages will be calculated using the number of patients from the FAS in each treatment group.

Primary SOCs will be sorted according to decreasing order of frequency in combined treatment group. Within each primary SOC, PTs will be sorted by decreasing frequency in combined treatment group.

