6.3. Data Handling Convention for Missing Data

For categorical variables, patients with missing data will be included in calculation of percentages. Number of patients with missing data will be presented

Handling of Medications with Missing/Partial Dates

To determine whether a medication is prior or concomitant medication, the missing medication start date is estimated as early as possible up to first dose date, and the missing medication end date is estimated as late as possible up to day 29. If the medication start date is missing, the onset day will not be imputed in medication listings.

Handling of AE Missing and Partial Start Dates

Every effort will be made to collect the start dates of all AEs. However, in the case the start date of an AE is incomplete or missing, it will be assumed to have occurred on or after the first dose of study medication, except if an incomplete date (e.g., month and year) clearly indicates that the event started prior to treatment. If the partial date indicates the same month or year of the first dose of study medication date, then the start date of the first dose will be imputed, otherwise, the missing day or month by the first day or the first month will be imputed.

Handling of Adverse events Severity and Relatedness

If the intensity of an SAE or AESI is missing, it will be classified as “Grade 3” in the frequency tables by CTC grade of SAE or AESIs. If the assessment of relationship of the investigational product is missing, it will be classified as related to the investigational product.

Date of infusion

Date of infusion is the non-missing administration date filled in the Drug Administration-Infusion CRF. If the first dose of study drug administration date is missing (even after site is queried), then the dosing date will be imputed with the randomization date. If any subsequent study drug administration date is missing, the date of dispensation of study drug from IRT will be used.

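### SAP 6.3 sets a fatal or life-threatening SAE with missing intensity to Grade 3 in the by-grade tables, and no grade 3-or-higher display is planned beside the grade 3–4 ones

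*Protocol*

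**What the plan says.** Protocol 10.2.4 grades adverse events 1 to 5, and Table 5 describes grade 5 as "Death related to adverse events". SAP Table 8 repeats the scale. Protocol 10.2.2 makes death a seriousness criterion that "includes all deaths, even those that appear to be completely unrelated to study drug", and Protocol 10.1.1 adds: "For deaths, the underlying or immediate cause of death should always be reported as an SAE". The sentence in 10.2.4, "TEAEs that are evaluated as CTCAE grade 3 or 4 will be collected in addition to treatment-emergent SAEs and treatment-emergent AESIs", is a collection rule; it defines no summary.

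The summaries are defined in SAP 5.7.1 and in the same terms in Protocol 11.4.10.1. The overview counts patients with "any TEAE, any SAE, any AESI, any serious AESI, any grade 3 or grade 4 TEAE, any fatal TEAEs", followed by withdrawal and infusion items. Among the tables by system organ class and preferred term, one is "Treatment-emergent grade 3 or 4 AEs presented by SOC and PT". Another covers all TEAEs by CTCAE grade with no restriction, and another covers all SAEs. Neither document plans a row or table for grade 3 or higher.

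SAP 6.3 handles missing grades: "If the intensity of an SAE or AESI is missing, it will be classified as" Grade 3, in the frequency tables by CTC grade. It makes no exception for outcome or seriousness criterion. Protocol 10.1.2 requires the investigator to report seriousness, severity and causality for every SAE and AESI.

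**The concern.** Two separate things look wrong.

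First, a single default grade is applied without regard to information already held. If an SAE is serious because the patient died, its grade on the trial's own scale is 5. If it is serious because it was life-threatening, the grade is 4. The rule enters 3 in both cases, so the by-grade table can contradict the seriousness data for the same event. The next sentence of SAP 6.3 treats missing relatedness as related, which is cautious. For a death, the Grade 3 default is the opposite of cautious.

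Second, a count limited to grades 3 and 4 does not rise steadily with severity. A patient whose only severe event was fatal is not in it. If a treatment turned some deaths into severe but survived events, this row would rise in the arm that did better. Deaths are expected in this population and are part of the primary clinical endpoint, so the row is easy to misread on its own. At stake is the reading of a few descriptive safety displays.

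**Working it through.** The documents give no grade distribution and no rate of missing grades, so there is no plan figure to reproduce. The check compares the rules and then uses assumed rates to show direction and scale.

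**Step 1: imputation rule against the grading scale.**

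| SAE with missing intensity | Grade on the trial's scale | Grade under SAP 6.3 | Shift |
|---|---|---|---|
| Fatal | 5 | 3 | 2 down |
| Life-threatening | 4 | 3 | 1 down |
| Any other | not determined | 3 | none shown |

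The life-threatening case moves an event within grades 3–4, so it alters the by-grade table but could not alter a grade 3–4 count.

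**Step 2: size of the imputation effect.** The largest safety pool is cohort 1 across phases 1, 2 and 3: 60 + 629 + 755 = 1444 patients, or 1444 / 3 ≈ 481 per arm. Assume 10% fatal events in one arm: 0.10 × 481 ≈ 48.

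| Share of grades missing (assumed) | Deaths entered at grade 3 | Deaths left at grade 5 | Fatal row if defined by outcome |
|---|---|---|---|
| 0% | 0 | 48 | 48 |
| 5% | 48 × 0.05 = 2.4, about 2 | 46 | 48 |
| 10% | 48 × 0.10 = 4.8, about 5 | 43 | 48 |
| 20% | 48 × 0.20 = 9.6, about 10 | 38 | 48 |

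The documents do not say whether a fatal TEAE is identified by outcome or by grade 5. If it were identified by an imputed grade, the fatal row would fall with the third column.

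**Step 3: the grade 3–4 row alone.** Classify each patient once, by worst grade. Assume placebo has 15% at worst grade 3–4 and 10% at grade 5, and that the active group moves s percentage points from grade 5 to grade 3–4.

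| s | Grade 3–4, placebo v active | Fatal, placebo v active | Grade 3 or higher, placebo v active |
|---|---|---|---|
| 2 | 15% v 17% | 10% v 8% | 25% v 25% |
| 4 | 15% v 19% | 10% v 6% | 25% v 25% |
| 6 | 15% v 21% | 10% v 4% | 25% v 25% |

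The grade 3–4 row moves against the active group, the fatal row moves for it, and the ordered count does not move.

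**Step 4: can the ordered count be rebuilt from the two planned rows?** If the rows count patients with any such event, a patient can be in both. Then grade 3 or higher = (grade 3–4) + (fatal) − (both), with the overlap anywhere from 0 to the smaller row. If the rows read 15% and 10% on placebo, the total lies between 15% and 25%. If they read 19% and 6% on active, it lies between 19% and 25%. The ranges overlap, so the two rows do not settle even the direction of the difference. The by-grade table would supply the total only if it carried a line for each patient's worst grade over all events, which the SAP does not specify.

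**The case against.** The strongest answer is that deaths are already well displayed. The fatal item sits directly after the grade 3–4 item in the same overview. The by-grade table has no upper limit. All deaths are SAEs, so the SAE row and SAE table keep fatal and non-fatal serious events together. The protocol's named safety endpoints are SAEs and grade 2 or higher infusion-related and hypersensitivity reactions, not this row. Safety is descriptive, with no test or decision attached, and percentages use all FAS patients, so nobody is removed from a denominator. This stands, and it limits the point to one row, one table and one imputation rule.

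A reader might infer that the severity summaries as a whole omit grade 5, so that an arm with fewer deaths is reported as less safe. The documents do not support that: anyone reading the overview sees the fatal row alongside. Nor does the grade 3–4 count always fall as deaths rise. A patient with another recorded grade 3–4 event stays in it, and the plan does not say whether an event that progresses to death is counted once at its worst grade.

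A reader might also infer that an ungraded death is counted in the overview's grade 3–4 row. SAP 6.3 confines the imputation to the tables by CTC grade, so that goes beyond the text. Required severity reporting should keep such cases few.

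One reply is only partly sufficient: that mortality is also analysed as efficacy. SAP 5.6 limits the efficacy analyses to phase 3 cohort 1, phase 2 cohort 1A and their pool. The safety tables in SAP 5.7 also cover phase 1/2 cohort 1 and cohorts 2 and 3. Those patients had an earlier phase 1/2 analysis, but safety data collected after that lock enter through these tables.

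**Conclusion.** The point holds in a limited form. Read as written, SAP 6.3 produces a wrong entry in the by-grade tables for any fatal or life-threatening SAE with missing intensity: two grades too low for a death, one for a life-threatening event. How many events this touches cannot be known from the documents and is probably small; the 2 to 10 deaths in Step 2 rest entirely on assumed death and missingness rates.

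The grade 3–4 row and its system-organ-class table are not ordered by severity when read alone, and the missing total cannot be recovered from the planned overview rows. The percentages in Step 3 are illustrations, with each patient classified once by worst grade; overlap between the rows would reduce the distortion. The fatal row, by-grade table and SAE tables prevent deaths from being hidden.

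This is a minor correction to descriptive safety tables. It changes no endpoint, test or efficacy estimate.

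**What to change.** - **SAP 6.3:** impute a missing intensity from the event's own seriousness criterion: death gives grade 5, life-threatening gives grade 4, and anything else keeps grade 3. Where both criteria apply, use the higher grade.
- **SAP 5.7.1 and Protocol 11.4.10.1:** state that a fatal TEAE is identified by its outcome, not by its grade.
- **Same sections:** add an overview row and a system-organ-class and preferred-term table for grade 3 or higher (grades 3 to 5), counting each patient once. Keep the by-grade table and the fatal row.

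The cost is a few sentences of text and minor programming. No new data are needed, because seriousness is already a required reporting item.

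While editing, reconcile a neighbouring conflict that decides what these tables contain: SAP 5.7 says grade 3 or 4 TEAEs are recorded in all phases, whereas Protocol 10.1.1 limits this to phase 1. Under the protocol's rule, the phase 2 and 3 entries would come from SAEs and AESIs only.

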10.2.5. Causality

The Investigator must provide causality assessment as whether or not there is a reasonable possibility that the drug caused the adverse event, based on evidence or facts, his/her clinical judgment, and the following definitions. The causality assessment must be made based on the available information and can be updated as new information becomes available.

The following factors should be considered when assessing causality:

- Temporal relationship: time to onset versus time drug was administered
- Nature of the reactions: immediate versus long term
- Clinical and pathological features of the events
- Existing information about the drug & same class of drugs
- Concomitant medications
- Underlying and concurrent illnesses
- Patient's medical and social history

Causality to the study drug (including study drug administration):

- Related:
 - The adverse event follows a reasonable temporal sequence from study drug administration and cannot be reasonably explained by the nature of the reaction, patient's clinical (eg, disease under study, concurrent diseases, concomitant medications), or other external factors.

or

- The adverse event follows a reasonable temporal sequence from study drug administration and is a known reaction to the drug under study or its class of drugs or is predicted by known pharmacology.
- Not Related:
 - The adverse event does not follow a reasonable sequence from study drug administration or can be reasonably explained by the nature of the reaction, patient's clinical state (eg, disease under study, concurrent diseases, and concomitant medications) or other external factors.

Causality to the study conduct (protocol specified procedure):

- Related:
 - The adverse event follows a reasonable temporal sequence from a protocol specified procedure and cannot be reasonably explained by the nature of the reaction, patient's clinical (eg, disease under study, concurrent diseases, concomitant medications), or other external factors.
- Not Related:
 - The adverse event does not follow a reasonable sequence from a protocol specified procedure or can be reasonably explained by the nature of the reaction, patient's clinical state (eg, disease under study, concurrent diseases, and concomitant medications) or other external factors.

10.3. Safety Monitoring

The investigator will monitor the safety of study patient at his/her site(s) as per the requirements of this protocol and consistent with current Good Clinical Practice (GCP). Any questions or concerns should be discussed with the Sponsor in a timely fashion. The Sponsor will monitor the safety data from across all study sites. The Medical/Study Director will have primary responsibility for the emerging safety profile of the compound, but will be supported by other departments (eg, Global Patient Safety; Biostatistics and Data Management). Safety monitoring will be performed on an ongoing basis (eg, individual review of SAEs) and on a periodic cumulative aggregate basis.

10.4. Notifying Health Authorities, Institutional Review Board, Ethics Committee, and Investigators

During the study, the Sponsor and/or the CRO will inform health authorities, ECs/Institutional Review Board (IRBs), and the participating investigators of any SUSARs (Suspected Unexpected Serious Adverse Reactions) occurring in other study centers or other studies of the active study drug, as appropriate per local reporting requirements. In addition, the Sponsor and/or CRO will comply with any additional local safety reporting requirements. All notifications to investigators will contain only blinded information.

Upon receipt of the Sponsor's notification of a SUSAR that occurred with the study drug, the investigator will inform the IRB/EC unless delegated to the Sponsor.

Event expectedness for study drug is assessed against the Reference Safety Information section of the Investigator's Brochure(s) that is effective for expedited safety reporting.

At the completion of the study, the Sponsor will report all safety observations made during the conduct of the trial in the Clinical Study Report to health authorities and ECs/IRB as appropriate.

11. STATISTICAL PLAN

This section provides the basis for the statistical analysis plans (SAPs) for the study. There will be separate SAPs for different portions of the study. The phase 1/2 SAP(s) specified the analysis for portions of phase 1 and phase 2 patients. The phase 1/2/3 SAP specifies the final efficacy and safety analyses for the remaining patients across all three study phases. The final SAPs will be issued before the first database lock in each portion of the study.

Endpoints are listed in Section 4. Analysis variables are listed in Section 5.

Overview of the Final Statistical Analysis Plan

This final SAP outlines the strategy and statistical methods to be used in the final analysis of data from all phases and all cohorts in the prematurely terminated study COV-2066, as below:

Efficacy Analysis

The efficacy analysis will be performed for the modified full analysis set (mFAS, defined in Section 11.3) of the following pooled cohort of patients and individual subsidiary cohorts, representing the totality of patients in this prematurely terminated study who were not unblinded in the database lock on 22 December 2020. In this document, the prematurely terminated phase 3 cohort 1 is referred as phase 3 cohort 1 and prematurely terminated phase 2 cohort 1A as phase 2 cohort 1A.

- Pooled phase 3 cohort 1 and phase 2 cohort 1A
- Phase 3 cohort 1
- Phase 2 cohort 1A

In each of these data sets (ie, the 2 prematurely terminated cohorts and the pooled cohort), the analyses will be conducted in the mFAS for the following patient populations. The mFAS is defined as patients that have a positive central-lab confirmed SARS-CoV-2 RT-qPCR result from an NP swab sample and the efficacy analysis was conducted in the mFAS to ensure detectable virus was present at baseline.

- Seronegative mFAS
- High Viral Load mFAS, where high viral load is defined as $>10^6$ copies/mL at baseline
- Overall mFAS

The **primary** virologic endpoint is time-weighted average change from baseline viral load in nasopharyngeal (NP) samples through Day 7. The primary analysis will be performed in the Seronegative mFAS population that is combined across the 2.4 g and 8g doses and pooled across phase 3 cohort 1 and phase 2 cohort 1A.

The **primary** clinical endpoint is death or mechanical ventilation. It will be estimated based on the proportion of patients who died or went on mechanical ventilation from Day 6 through Day 29, where events occurring during the first 5 days will be excluded because of the notion that clinical impact would occur only after achieving several days of viral suppression. This observation was noted in the analysis of data from phase 1/2 portion of this study. In addition, the endpoint of death or mechanical ventilation from Day 1 through Day 29 will also be evaluated. The primary analysis will be performed for the High Viral Load mFAS, Seronegative mFAS, and the Overall mFAS in the pooled phase 3 cohort 1 and phase 2 cohort 1A and combined across the 2.4 g and 8 g doses of REGN10933+REGN10987. To control alpha at a strict 0.05 level, the two primary endpoints will be tested hierarchically, with the virologic endpoint tested first.

Safety Analysis

The safety analysis will be performed for the following cohorts, separately. Patients in phase 1/2 cohort 1, phase 2 cohort 2 and cohort 3 are included into the analysis because more safety data were collected for the patients after the database lock on 22 December 2020.

- Phase 2 cohort 1A
- Phase 2 cohort 2
- Phase 2 cohort 3
- Phase 1/2/3 cohort 1 combined

Pharmacokinetics (PK) and Immunogenicity Analysis

The PK and ADA analysis will be performed for phase 1/2/3 cohort 1 combined, phase 2 cohort 1A, phase 2 cohort 2, and phase 2 cohort 3, separately. The NAb analysis will be performed for phase 2/3 patients.

